### 10.3. Criteria for Treatment-Emergent Potentially Clinical Significant Value for Pediatric Patients

Parameter	Treatment Emergent PCSV 	Comments
Clinical Chemistry		
ALT	>3 and ≤ 5 ULN and baseline ≤ 3 ULN* >5 and ≤ 10 ULN and baseline ≤ 5 ULN >10 and ≤ 20 ULN and baseline ≤ 10 ULN >20 ULN and baseline ≤ 20 ULN	Enzyme activity must be expressed in ULN, not in IU/L. Concept paper on DILI – FDA draft Guidance Oct 2007. Each category is calculated independently.
AST	>3 and ≤ 5 ULN and baseline ≤ 3 ULN* >5 and ≤ 10 ULN and baseline ≤ 5 ULN >10 and ≤ 20 ULN and baseline ≤ 10 ULN >20 ULN and baseline ≤ 20 ULN	Enzyme activity must be expressed in ULN, not in IU/L. Concept paper on DILI – FDA draft Guidance Oct 2007. Each category is calculated independently.
Alkaline Phosphatase	>1.5 ULN and baseline ≤ 1.5 ULN	Enzyme activity must be expressed in ULN, not in IU/L. Concept paper on DILI – FDA draft Guidance Oct 2007.
Total Bilirubin	≥1.3 ULN and baseline < 1.3 ULN	Must be expressed in ULN, not in μmol/L or mg/L. Based on normal range: <1 mg/dL, CF = mg x 1.7 = μmol Concept paper on DILI – FDA draft Guidance Oct 2007.
Conjugated Bilirubin	(Direct Bilirubin >35% Total Bilirubin and Total Bilirubin ≥1.3 ULN)	Conjugated bilirubin will be measured when the total bilirubin is above the ULN Based on normal range: 0 to 0.4 mg/dL
ALT and Total Bilirubin	(ALT ≥3 ULN and TBILI ≥2 ULN) and baseline (ALT <3 ULN or TBILI <2 ULN)	Concept paper on DILI – FDA draft Guidance Oct 2007.
CPK	≥3 ULN and baseline < 3ULN	FDA Feb 2005. Am J Cardiol April 2006.
Creatinine	≥132μmol/L and baseline < 132μmol/L (or ≥1.5 mg/dL and baseline <1.5 mg/dL)  >=30% change from baseline	Benichou C., 1994 Two independent criteria

 The ULN is based upon central lab reference ranges. The reference range might be different for different age-groups. For the purpose of this study in a particular patient the reference range based upon age at baseline will be used as reference throughout the study for determining PCSVs

Parameter	Treatment Emergent PCSV 	Comments
Uric Acid		
Hyperuricemia	>8.0 mg/dL and ≤8.0 mg/dl at baseline (or >476 μmol/L and ≤476 μmol/L at baseline)	
Hypouricemia	≤2 mg/dL and >2 mg/dL at baseline (or ≤119 μmol/L and baseline > 119 μmol/L)	
Blood Urea Nitrogen	≥20 mg/dL and <20 mg/dL at baseline (or ≥7.14 mmol/L and <7.14 mmol/L at baseline)	
Chloride		Two independent criteria
Hypochloremia	<80 mmol/L and baseline ≥ 80 mmol/L	Reference ranges are same in adolescents (12-17 yrs. old) and adults
Hyperchloremia	≥115 mmol/L and baseline < 115 mmol/L	
Sodium		Two independent criteria
Hyponatremia	<129 mmol/L and baseline ≥ 129 mmol/L	Reference ranges are similar in adolescents (12-17 yrs. old) and adults
Hypernatremia	≥150 mmol/L and baseline <150 mmol/L	
Potassium		FDA Feb 2005.
Hypokalemia	≤3.5 mmol/L and baseline >3.5 mmol/L	Two independent criteria
Hyperkalemia	≥5.5 mmol/L and baseline <5.5 mmol/L	Reference ranges are similar in adolescents (12-17 yrs. old) and adults
Calcium total	<2 mmol/L and baseline ≥2 mmol/L (or ≤ 8 mg/dL and baseline >8 mg/dL) ≥2.9 mmol/L and baseline <2.9 mmol/L (or ≥11.6 mg/dL and baseline <11.6 mg/dL)	
LDL Cholesterol	≥4.91 mmol/L and <4.91 mmol/L at baseline (≥ 190 mg/dl and <190 mg/dl at baseline)	Threshold for therapeutic intervention with pharmacotherapy in children (Expert Panel on Integrated Guidelines for Cardiovascular Health and Risk Reduction in Children and Adolescents; 2011).
Total cholesterol	≥6.20 mmol/L and < 6.20 mmol/L at baseline (or ≥ 240 mg/dL and < 240 mg/dL at baseline)	
Triglycerides	Fasting level ≥ 5.64 mmol/L and < 5.64 mmol/L at baseline (or ≥ 500 mg/dL and < 500 mg/dL at baseline)	Threshold for therapeutic intervention with pharmacotherapy in children. (Expert Panel on Integrated Guidelines for Cardiovascular Health and Risk Reduction in Children and Adolescents; 2011). CF = g x 1.14 = mmol
Glucose		
Hypoglycaemia	<2.7 mmol/L and ≥2.7 mmol/L at baseline (or < 50 mg/dL and ≥ 50 mg/dL at baseline)	
Hyperglycaemia	≥10 mmol/L (unfasted) and < 10 mmol/L (unfasted) at baseline (or ≥180 mg/dl and <180 mg/dl at baseline); ≥7 mmol/L (fasted) and <7 mmol/L (fasted) at baseline (or ≥120 mg/dL and <120 mg/dL at baseline)	

Parameter	Treatment Emergent PCSV 	Comments
HbA1c	>6.5% and ≤ 6.5% at baseline	WHO 2006/2011 ADA 2003 and 2012
Albumin	≤25 g/L and >25 g/L at baseline	Reference ranges are same in children (6-17 yrs. old) and adults
Hematology		
WBC	<4.0 Giga/L and ≥4.0 Giga/L at baseline >13.5 Giga/L and ≤13.5 Giga/L at baseline	
Lymphocytes	<0.6 Giga/L and ≥0.6 Giga/L at baseline >6.0 Giga/L and ≤6.0 Giga/L at baseline	
Neutrophils	<1.2 Giga/L and ≥1.2 Giga/L at baseline >ULN and baseline ≤ ULN	International Consensus meeting on drug-induced blood cytopenias, 1991. FDA criteria.
Monocytes	>1.2 Giga/L and ≤ 1.2 Giga/L at baseline	
Eosinophils	(>0.5 Giga/L and >ULN) and (≤0.5 Giga/L or ≤ ULN at baseline)	Harrison- Principles of internal Medicine 17 th Ed., 2008.
Hemoglobin	<10 g/dL and >10 g/dL at baseline (or <100 g/L and ≥100 g/L at baseline) ≥20 g/dL and <20 g/dL at baseline (or ≥200 g/L and <200 g/L at baseline)	Two criteria are independent
Hematocrit	For males: <0.37 v/v and ≥0.37 v/v at baseline; >0.52 v/v and ≤0.52 v/v at baseline For females: <0.33 v/v and ≥0.33 v/v at baseline <0.47 v/v and ≥0.47 v/v at baseline	Two Criteria are independent
Platelets	<100 Giga/L and ≥100 Giga/L at baseline >700 Giga/L and ≤ 700 Giga/L at baseline	International Consensus meeting on drug-induced blood cytopenias, 1991. Two independent criteria

Parameter	Treatment Emergent PCSV 	Comments
Urinalysis		
Ketonuria	Presence and absence at baseline	Semi-quantitative methods
Glycosuria	Presence and absence at baseline	Semi-quantitative methods
Microscopic Hematuria	> 5 RBCs/ HPF and ≤5 RBCs/ HPF at baseline	Semi-quantitative methods
Proteinuria	≥ 1+ and <1 at baseline	Semi-quantitative methods, ≥ 1+ means concentration ≥30 mg/dL
Vital signs		
HR	≤50 bpm and decrease from baseline ≥20 bpm ≥120 bpm and increase from baseline ≥20 bpm	
SBP	Hypotension: SBP < 5 th percentile for gender, age and height; baseline ≥ 5 th percentile and decrease from baseline ≥ 20 mmHg  Hypertension: At or above the 95 th percentile for age, sex and height postbaseline; baseline < 95 th percentile; and increase from baseline ≥ 20 mmHg	Based on definition of hypotension as SBP < 5 th percentile for gender, age and height  Based on definition of Hypertension as average SBP ≥ 95 th percentile for gender, age, and height on ≥ 3 occasions
DBP	Hypotension: DBP < 5 th percentile for gender, age and height; baseline ≥ 5 th percentile and decrease from baseline ≥ 10 mmHg  Hypertension: At or above the 95 th percentile for age, sex and height postbaseline; baseline < 95 th percentile and increase from baseline ≥ 10 mmHg	Based on definition of Hypertension as average DBP ≥ 95 th percentile for gender, age, and height on ≥ 3 occasions
Temperature	Rectal, ear: >100.4 °F/38.0 °C Oral: >99.5 °F/37.5 °C Axillary: >99 °F/37.2 °C	
Respiratory rate	<12 per minute and ≥12 per minute at baseline  >20 per minute and ≤20 per minute at baseline	
Weight	≥5% decrease from baseline	Based on identification of trends in the child's growth with a series of visits WHO Multicentre Reference Study Group, 2006; Center for Disease Control. Growth chart 2007.
ECG		Ref.: CPMP 1997 guideline.
HR	≤50 bpm and decrease from baseline ≥20 bpm ≥120 bpm and increase from baseline ≥20 bpm	
PR	≥200 ms and < 200 ms at baseline	
QRS	≥110 ms & < 110 ms at baseline	

Parameter	Treatment Emergent PCSV 	Comments
QTc	Absolute values (ms) Borderline: 431-450 ms and < 431 ms at baseline for Male; 451-470 ms and < 451 ms at baseline for Female  Prolonged: >450 to <500 ms and <= 450 ms at baseline for Male; >470 to <500 ms and <= 470 ms at baseline for Female  Additional: ≥500 ms and < 500 ms at baseline  Increase from baseline Borderline: Increase from baseline 30-60 ms Prolonged: Increase from baseline >60 ms	Bazett's formula (measured QT interval divided by the square root of the R-R) to be applied to arrive at corrected QT value interval)  QTc prolonged and ΔQTc > 60 ms are the PCSA to be identified in individual subjects/patients listings.  independent criteria

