#### 5.4.2.1. Reasons for Permanent Discontinuation of Study Drug

Study drug dosing will be permanently discontinued in the event of:

- Anaphylactic reaction or other severe systemic reaction to study drug
- Repeated (2 or more during the course of the study) severe injection site reactions that are deemed to be immune mediated\*

\* This is based on investigator's assessment. A consultation with the medical monitor can be sought to determine the exact etiology of an injection site reaction.

- Diagnosis of a malignancy during study
- Evidence of pregnancy
- Any infection that is opportunistic, such as active tuberculosis and other infections whose nature or course may suggest an immuno-compromised status
- Severe laboratory abnormalities:
  - Neutrophil count  $\leq 0.5 \times 10^3/\mu\text{L}$
  - Platelet count  $\leq 50 \times 10^3/\mu\text{L}$
  - ALT and/or AST values greater than  $3 \times \text{ULN}$  with total bilirubin  $> 2 \times \text{ULN}$  (unless elevated bilirubin is related to confirmed Gilbert's Syndrome)
  - Confirmed AST and/or ALT  $> 5 \times \text{ULN}$  (for more than 2 weeks)

NOTE: If the laboratory abnormality is considered causally related to study drug, study treatment will be permanently discontinued. In cases in which a causal relationship to study drug can be reasonably excluded, (ie, an alternative cause is evident), study treatment will be discontinued but it may be resumed when the laboratory abnormality is sufficiently normalized. A decision to resume study treatment will be made jointly by the investigator and medical monitor (medical monitor's written approval is required).

- Treatment with any prohibited concomitant medication or procedure (section 5.7.1)

**NOTE: The use of TCS, TCI and crisaborole is prohibited during the study. However, these drugs may be used as rescue. In that case, the study drug will be continued.**

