#### 5.4.2.2. Reasons for Temporary Discontinuation of Study Drug

Study drug dosing may be temporarily discontinued in the event of:

- Clinically important laboratory abnormalities, such as:
  - ALT or AST  $3 \times$  ULN
  - Neutrophil count  $<1.5 \times 10^3/\mu\text{L}$  but  $>0.5 \times 10^3/\mu\text{L}$
  - Platelet count  $\leq 100 \times 10^3/\mu\text{L}$  but  $>50 \times 10^3/\mu\text{L}$
  - CPK  $>5 \times$  ULN
  - Serum creatinine  $>1.5 \times$  ULN
- Other intercurrent illnesses or major surgery
- An infection that requires parenteral treatment with antibiotic, antifungal, antiviral, antiparasitic, or antiprotozoal agents, or requires oral treatment with such agents for longer than 2 weeks

After the condition leading to suspension of dosing normalizes sufficiently, study treatment may resume at the discretion of the principal investigator in consultation with the medical monitor. A decision to discontinue study drug and/or to reinstitute study treatment should be discussed with the medical monitor. The investigator may suspend study treatment at any time, even without consultation with the medical monitor, if the urgency of the situation requires immediate action and if this is determined to be in the patient's best interest. However, the medical monitor should be contacted as soon as possible in any case of study drug discontinuation. Resumption of study treatment after temporary discontinuation should always be discussed with the medical monitor.

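### SAP 10.3's combined liver flag pairs bilirubin with ALT only, so an AST-driven case meeting the protocol's severe liver criterion is not counted as a combined case

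*SAP*

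**What the plan says.** **Liver.** Among the severe laboratory abnormalities in protocol section 5.4.2.1 is "ALT and/or AST values greater than" 3 × ULN with total bilirubin above 2 × ULN, "unless elevated bilirubin is related to confirmed Gilbert's Syndrome". A separate line covers "Confirmed AST and/or ALT" above 5 × ULN for more than two weeks.

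SAP section 10.3 defines the treatment-emergent potentially clinically significant values (PCSVs). ALT and AST each have four bands, starting above 3, 5, 10 and 20 × ULN. Total bilirubin has a single threshold at 1.3 × ULN. Only one row pairs a transaminase with bilirubin, and its full condition is "ALT ≥3 ULN and TBILI ≥2 ULN) and baseline (ALT <3 ULN or TBILI <2 ULN".

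**Neutrophils.** Protocol section 5.4.2.2 opens with "Study drug dosing may be temporarily discontinued in the event of" and introduces its laboratory examples as "Clinically important laboratory abnormalities, such as" a neutrophil count below 1.5 but above 0.5 × 10³/µL. Section 5.4.2.1 puts 0.5 or below among the severe abnormalities. The SAP's low-neutrophil flag is "<1.2 Giga/L and ≥1.2 Giga/L at baseline", with no further banding.

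**The concern.** A combined transaminase and bilirubin row exists to show whether both rises occurred in one patient, and readers of the safety tables will look there first for serious liver injury. As defined, the row can show zero while the trial contains a patient at the levels the protocol itself calls severe, if AST rather than ALT drove the case. Neither document explains why AST was left out of this row when it has its own graded row in the same appendix.

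The neutrophil point is smaller. The flag does not line up with the two levels named in protocol section 5.4.2, so the PCSV table cannot be read directly against pauses and stops.

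**Working it through.** The plan gives no figure here to reproduce. The check is whether values that satisfy the protocol's criterion also satisfy the SAP flag.

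**Step 1. The rules side by side (multiples of ULN)**

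| | Protocol 5.4.2.1 | SAP 10.3 combined row |
|---|---|---|
| Enzyme | ALT >3 or AST >3 | ALT ≥3 |
| Total bilirubin | >2 | ≥2 |
| Gilbert's exception | yes | no |

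**Step 2. One assumed patient.** Baseline: ALT and AST 1, bilirubin 0.8. Later: AST 4, ALT 2.5, bilirubin 2.5.

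- Protocol: AST 4 > 3 and bilirubin 2.5 > 2, so the levels are met.
- SAP combined row: ALT 2.5 < 3, so it is not met.
- SAP single rows: the first AST band and the bilirubin row (2.5 ≥ 1.3) are both met.

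**Step 3. A grid.** The baseline is as in step 2, with no Gilbert's cases. ALT and AST each take 11 values: 1, 2, 2.9, 3, 3.1, 4, 5, 5.1, 8, 12, 25. Bilirubin takes 7: 0.8, 1.2, 1.3, 1.9, 2, 2.1, 3.

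- Meeting the protocol's levels: 11 × 11 − 4 × 4 = 105 enzyme pairs with at least one above 3. Two bilirubin values exceed 2, so 105 × 2 = 210.
- Of these, missed by the combined row: ALT <3 (3 values) × AST >3 (7 values) × 2 = 42, all AST-driven.
- Of the 42, missed by every PCSV row: 0. Each triggers the AST row and the bilirubin row.
- Meeting the combined row: ALT ≥3 (8) × AST (11) × bilirubin ≥2 (3) = 264. Of these, 210 − 42 = 168 meet the protocol's levels and 264 − 168 = 96 do not. The row is therefore also wider than the protocol in places.
- With AST added at the SAP's own cut-offs: every point with an enzyme above 3 and bilirubin above 2 qualifies, so 0 of 210 are missed.

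The ratio 42/210 depends on the grid values chosen and is not a probability.

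**Step 4. What the single rows can show.** They count patients per parameter, so they do not show that AST and bilirubin rose in the same patient. The bilirubin row has no category at 2 × ULN. It also requires a baseline below 1.3 × ULN. A patient going from bilirubin 1.5 to 2.5 with AST 4 and ALT 2.5 triggers the AST row but not the total bilirubin row; the conjugated bilirubin row would apply only if the direct fraction exceeded 35%.

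**Step 5. The baseline side.** The present baseline condition is the negation of the combined criterion: not (ALT ≥3 and TBILI ≥2) equals ALT <3 or TBILI <2. With AST included, not ((ALT ≥3 or AST ≥3) and TBILI ≥2) equals (ALT <3 and AST <3) or TBILI <2.

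**Step 6. Neutrophils (1 Giga/L = 1 × 10³/µL; baseline assumed ≥1.2).** Counts from above 0.5 to below 1.2 are flagged, and so are counts of 0.5 or below. Counts from 1.2 to below 1.5 fall within the pause criterion but raise no PCSV: (1.5 − 1.2)/(1.5 − 0.5) = 0.30 of the width of that range, which is not a share of patients.

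**The case against.** The strongest reply is that PCSV flags and dosing rules serve different purposes. Protocol section 9.5.3.2 leaves the PCSV criteria to the SAP and does not require them to match section 5.4.2. SAP 10.3 cites its own sources for both the combined liver row and the neutrophil row, and whether those sources support ALT alone, or 1.2, cannot be judged from these documents. The appendix does not follow the dosing rules in either direction: CPK is flagged from 3 × ULN against a possible pause above 5 × ULN. All of this stands. It means the two documents do not contradict each other, and it makes the neutrophil bands largely a matter of preference.

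A reader might go further and infer that events which make a site stop or pause study drug are missing from the safety tables. The documents do not support that:

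- With normal baselines, every AST-driven case reaches the AST and bilirubin rows.
- SAP section 5.8.2 lists all laboratory parameters by patient and visit, and section 5.4 tabulates treatment discontinuation by reason.
- Neutrophil counts at 0.5 or below lie inside the flag when baseline is at least 1.2. Exclusion criterion 19 rejects confirmed screening counts below 1.5, so a lower baseline should be unusual.
- A pause between 1.2 and 1.5 is permitted, not required.

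These outputs are still not a full substitute for the combined row. A listing shows co-occurrence only to someone who searches it. Under the note in protocol 5.4.2.1, treatment may resume when a causal relationship is reasonably excluded, and SAP section 5.8.1 summarises only adverse events leading to permanent discontinuation. Such a patient could be in neither that table nor the combined row.

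**Conclusion.** The point holds for the liver row. SAP 10.3 omits AST from its only combined transaminase and bilirubin flag, so an AST-driven case at the levels the protocol calls severe is not counted as a combined case. The row is not simply narrower than the protocol rule: on the ALT side it is slightly wider.

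The size in patients is unknown, because the documents give no expected frequency. One hypothetical case among about 160 dupilumab patients would be 1/160 = 0.6%, but that illustrates the scale of a single count and is not an estimate. No hypothesis test or efficacy result is affected. The grid result assumes normal baselines and no Gilbert's cases; the single-row cover is weaker when baseline bilirubin is already 1.3 × ULN or more.

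The neutrophil mismatch is real but minor. It touches an optional pause and the lack of a separate category at 0.5 or below; with baseline at least 1.2, no count at the stop level goes unflagged. It has some practical effect. Protocol section 7.2.5 does not treat a protocol-stipulated dose adjustment as a ground for reporting a laboratory value as an adverse event, and the SAP has no table of temporary discontinuations, so a pause at 1.2 to below 1.5 may have no event count. No view is taken on which threshold is clinically right.

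**What to change.** In SAP 10.3, redefine the combined liver row:

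- Post-baseline: `(ALT ≥3 ULN or AST ≥3 ULN) and TBILI ≥2 ULN`
- Baseline: `(ALT <3 ULN and AST <3 ULN) or TBILI <2 ULN`

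AST and bilirubin are already in the chemistry panel (protocol section 6.2.3.5), so the cost is one reworded row and its programming. Dosing rules are unaffected. One pattern moves the other way: a patient with AST ≥3, ALT <3 and bilirubin ≥2 × ULN at baseline, whose ALT later reaches 3 × ULN with bilirubin still ≥2, is counted today and would not be under the new row. Exclusion criterion 18, on persistently raised transaminases, should make that rare.

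Optionally, reconcile the neutrophil summary with protocol section 5.4.2 by adding categories at the levels already named there (below 1.5, and 0.5 or below) while keeping below 1.2, or state in the SAP why they differ. This costs two extra rows or one sentence.

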## 5.8. Analysis of Safety Data

The summary of safety and tolerability will be performed based on SAF.

The safety analysis will be based on the reported AEs, clinical laboratory evaluations, physical examination, vital signs and 12-lead ECG.

Thresholds for treatment-emergent Potentially Clinically Significant Values (PCSVs) in laboratory variables and vital signs are defined in [Appendix 10.3](#). Treatment-emergent PCSV is any PCSV developed or worsened in severity compared to the baseline during the treatment and follow-up period.

The time interval to detect any event or abnormality is between the first injection of study medication and EOS.

Subgroups are defined by key baseline factors recorded on the CRF and listed to be considered for safety analyses:

- Age group ( $\geq 12$  to  $< 15$ ,  $\geq 15$  to  $< 18$ )
- Sex (Male, Female)
- Ethnicity (Hispanic or Latino (no/yes))
- Race (White, Black, Asian, Other)
- Duration of AD ( $< 13$  years,  $\geq 13$  years)
- Baseline BMI group (overweight:  $\geq 85$  percentile of general population based on age and gender,  $< 85$  percentile)
- Baseline weight group ( $< 60$  kg,  $\geq 60$  kg)

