### **5.8.2. Analysis of Clinical Laboratory Measurements**

Laboratory measurements include clinical chemistry, hematology and urinalysis results, and will be converted to standard international units and US conventional units. Summaries of laboratory variables will include:

- Descriptive statistics of laboratory result and change from baseline by visit
- The number (n) and percentage (%) of patients with abnormal lab value during study whose screening and baseline values are normal (overall and per each lab parameter)
- The number (n) and percentage (%) of patients with treatment-emergent PCSVs overall during the study, during the treatment period and during the follow-up period
- Shift tables based on baseline normal/abnormal and other tabular and graphical methods may be used to present the results for parameters of interest

Listing of all laboratory parameters normal range, abnormal flag and treatment-emergent PCSV by patient and visit will be provided.

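### The fasted-glucose safety flag is set at 7 mmol/L or 120 mg/dL, which are different concentrations, and the SAP does not say which unit governs

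*SAP*

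**What the plan says.** SAP 10.3 gives three glucose criteria, each in both units:

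- Hyperglycaemia, fasted: "≥7 mmol/L (fasted) and <7 mmol/L (fasted) at baseline (or ≥120 mg/dL and <120 mg/dL at baseline".
- Hyperglycaemia, unfasted: "≥10 mmol/L (unfasted) and < 10 mmol/L (unfasted) at baseline (or ≥180 mg/dl and <180 mg/dl at baseline".
- Hypoglycaemia: "<2.7 mmol/L and ≥2.7 mmol/L at baseline (or < 50 mg/dL and ≥ 50 mg/dL at baseline".

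These criteria are the operative definition. SAP 5.8 states: "Thresholds for treatment-emergent Potentially Clinically Significant Values (PCSVs) in laboratory variables and vital signs are defined in" Appendix 10.3, and protocol section 9.5.3.2 leaves the PCSV criteria to the SAP.

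SAP 5.8.2 says that laboratory measurements "will be converted to standard international units and US conventional units". It then lists one PCSV summary: "The number (n) and percentage (%) of patients with treatment-emergent PCSVs overall during the study, during the treatment period and during the follow-up period". A by-patient listing also carries the PCSV flag. Neither 5.8.2 nor the data conventions in SAP section 6 say which unit is used to derive it.

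**The concern.** When a criterion is written as one figure with its equivalent in another unit, the two must be the same quantity. Otherwise the criterion contains two cut-offs, and the plan has not fixed which applies. Here a programmer could apply the mmol/L figure, apply the mg/dL figure, or read the word between them literally and flag a patient who meets either. These choices can give different answers for the same patient.

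At stake is the reproducibility of one safety count. Two programmers working correctly from the same SAP could report different numbers of patients with a treatment-emergent glucose PCSV, and nothing in the plan would show which number was intended.

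**Working it through.** **Inputs.** All come from the glucose rows of SAP 10.3: 10 mmol/L with 180 mg/dL (unfasted), 7 mmol/L with 120 mg/dL (fasted), and 2.7 mmol/L with 50 mg/dL (hypoglycaemia).

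**Step 1: the factor implied by each pair** (mg/dL divided by mmol/L). One analyte has one factor, so the three should agree.

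- Unfasted: 180 / 10 = 18.0
- Fasted: 120 / 7 = 17.14
- Hypoglycaemia: 50 / 2.7 = 18.52

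**Step 2: convert the fasted pair.** With the factor of 18 from the same cell:

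- 7 x 18 = 126 mg/dL, not 120. The gap is 6 mg/dL, and 6 / 120 = 5%.
- 120 / 18 = 6.67 mmol/L, not 7.

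The printed 120 is not recovered with the other factors tried. The molar mass of glucose (180.156 g/mol, a physical constant taken from outside the documents) gives 18.0156, hence 126.1 mg/dL and 6.66 mmol/L. The hypoglycaemia pair's own 18.52 gives 129.6 mg/dL and 6.48 mmol/L.

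**Step 3: convert the hypoglycaemia pair.** 2.7 x 18 = 48.6 mg/dL against 50 printed, a gap of 1.4 mg/dL (1.4 / 48.6 = about 3%). Conversely, 50 / 18 = 2.78 mmol/L.

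**Step 4: is this the table's usual rounding?** Where the table gives two pairs for one analyte, or for two measures of the same substance, the implied factors can be compared without outside figures:

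- Uric acid: 476 / 8 = 59.5 and 119 / 2 = 59.5.
- Calcium: 8 / 2 = 4.0 and 11.6 / 2.9 = 4.0.
- LDL and total cholesterol: 190 / 4.91 = 38.7 and 240 / 6.20 = 38.7.

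One row is slightly off by its own printed factor. Triglycerides of 500 mg/dL are 5 g/L, and 5 x 1.14 = 5.70 mmol/L against 5.64 printed, about 1%. The 5% in the fasted glucose pair is well outside that.

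**Step 5: who is classified differently?** The fasted criterion requires a post-baseline value at or above the threshold and a baseline below it.

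| Fasted baseline to post-baseline, mmol/L | Same values, mg/dL (x 18) | Flagged at 7 mmol/L | Flagged at 120 mg/dL |
|---|---|---|---|
| 5.5 to 6.8 | 99 to 122.4 | no | yes |
| 6.8 to 7.2 | 122.4 to 129.6 | yes | no (baseline already above 120) |
| 6.72 to 6.89 | 121 to 124 | no | no (baseline already above 120) |
| 5.5 to 7.2 | 99 to 129.6 | yes | yes |
| 5.5 to 6.5 | 99 to 117 | no | no |

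The two units can disagree only if the baseline or the post-baseline value lies from 120 to below 126 mg/dL (6.67 to below 7.0 mmol/L). The disagreement can go either way, because the baseline condition uses the same mismatched figures. If the criterion is read as flagging a patient who meets either form, the first two rows are both flagged, which is a third possible count.

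For hypoglycaemia the band is 48.6 to below 50 mg/dL (2.7 to below 2.78 mmol/L). A post-baseline value in the band, with a baseline of 50 mg/dL or more, is flagged only in mg/dL. A baseline in the band followed by a value below 48.6 mg/dL is flagged only in mmol/L.

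**The case against.** The arithmetic is hard to dispute. The strongest reply is that it may change little, or nothing, in the output.

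**Fasting.** The larger mismatch bears only on results classed as fasted. Neither the schedules of events (protocol 6.1, SAP 10.2) nor the laboratory sections (protocol 6.2.3.5, SAP 4.5.2) state a fasting requirement or provide for recording fasting status. For glucose, the distinction appears only in SAP 10.3. The laboratory manual, which is not among the documents, may cover it. This stands: the number of patients affected is unknown and could be zero. The hypoglycaemia mismatch does not depend on fasting, but its band is only 1.4 mg/dL wide.

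**Separate tables.** A reader might infer from the conversion into both unit systems that SI and US-unit PCSV tables will be produced and will contradict each other. SAP 5.8.2 does not support that. It plans one PCSV count, and the gap is that the unit behind it is not named.

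**Every value in the band.** A reader might also infer that any fasted result from 120 to below 126 mg/dL is flagged in mg/dL and missed in mmol/L. The baseline condition rules this out, as the second and third rows of the table show.

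**Rounding.** It can be said that 7 is 6.67 rounded to a whole number. That could explain how the pair arose, but it does not cure it: a program would apply the printed 7, and the same table prints other mmol/L thresholds to one or two decimals. Rounding does not explain the hypoglycaemia pair, since 2.78 to one decimal is 2.8, not 2.7.

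**Conclusion.** The fasted pair is wrong as written. The two printed thresholds differ by 5%, so at most one of them can be the intended criterion. Because no governing unit is named, the treatment-emergent glucose PCSV count is not fully specified for patients with a fasted baseline or post-baseline value from 120 to below 126 mg/dL. The hypoglycaemia pair has the same fault on a smaller scale, over 48.6 to below 50 mg/dL.

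This rests on the factor of 18 in the table's own unfasted pair, and using the molar mass of glucose instead does not change it. The documents do not allow an estimate of how many patients fall in either band.

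It would be tempting to conclude that 120 is simply a misprint for 126. The documents do not settle that. 120 mg/dL with 6.67 mmol/L is an equally consistent pair, and the table does not treat one unit system as primary, since uric acid and blood urea nitrogen are given in mg/dL first.

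The consequence is limited to glucose PCSV counts and listing flags. No efficacy endpoint, hypothesis test or sample size is affected. It is a minor point, worth correcting because the correction is so cheap.

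**What to change.** In SAP 10.3, choose one threshold for each of the two criteria and print its exact conversion:

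- Fasted hyperglycaemia: 7 mmol/L with 126 mg/dL, or 120 mg/dL with 6.67 mmol/L.
- Hypoglycaemia: 2.7 mmol/L with 48.6 mg/dL, or 50 mg/dL with 2.78 mmol/L.

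Which threshold to keep is for the sponsor. Then add one sentence to SAP 5.8.2 or 10.3 naming the unit in which PCSV flags are derived, so that rounding between unit systems cannot move a patient across a cut-off. Either unit will do.

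The cost is one figure in each of two table entries and one sentence, made before database lock. Data collection and the other analyses are unchanged.

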#### ***PCSV***

Patients who had post-baseline PCSV but missing baseline value will be regarded as having treatment emergent PCSV.

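### SAP Appendix 10.3: the second female hematocrit PCSV rule has both inequality signs reversed, so it misses rises above 0.47 and flags falls below it

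*SAP*

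**What the plan says.** Protocol 9.5.3.2 leaves the laboratory PCSV criteria to the SAP. SAP 5.8 places them in Appendix 10.3 and adds the general definition: "Treatment-emergent PCSV is any PCSV developed or worsened in severity compared to the baseline during the treatment and follow-up period". SAP 5.8.2 then reports the number and percentage of patients with treatment-emergent PCSVs by period. Appendix 10.3 is therefore the text a programmer will code from.

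The hematocrit row of Appendix 10.3 has four lines:

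- Males, first line: below 0.37 with baseline at or above 0.37.
- Males, second line: ">0.52 v/v and ≤0.52 v/v at baseline".
- Females, first line: below 0.33 with baseline at or above 0.33.
- Females, second line: "<0.47 v/v and ≥0.47 v/v at baseline".

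The comment column says that the two criteria are separate from each other. For patients without a baseline, SAP 6.3 adds: "Patients who had post-baseline PCSV but missing baseline value will be regarded as having treatment emergent PCSV".

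Elsewhere in the table, many limits are given in two unit systems. For fasted hyperglycaemia the pair is "≥7 mmol/L (fasted) and <7 mmol/L (fasted) at baseline (or ≥120 mg/dL and <120 mg/dL at baseline". SAP 5.8.2 converts results to both SI and US units but does not say which governs the flag.

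**The concern.** Both female hematocrit lines point downward. The row therefore has no rule that detects a high value in a female, although it has one for males. The second female line instead flags a fall from 0.47 or above to anything below 0.47.

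Safety is the study's secondary objective, and the PCSV table is one of its standard laboratory summaries. If the cell is coded literally, female high-hematocrit cases drop out of the PCSV count and harmless falls can enter it. The female count would then not measure the same thing as the male count.

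**Working it through.** **Which direction was meant?** Three features of the table answer this.

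1. *Pattern of paired rows.* WBC (4.0 and 13.5), lymphocytes (0.6 and 6.0), platelets (100 and 700) and male hematocrit (0.37 and 0.52) all have the form: below x with baseline at or above x, then above y with baseline at or below y. Flipping both signs in the second female line gives exactly this form.
2. *Ordering of limits.* As high limits, 0.47 (female) lies below 0.52 (male), just as the low limits 0.33 (female) lie below 0.37 (male). As a low limit, 0.47 for females would sit above the male low limit of 0.37.
3. *Redundancy.* The low direction for females is already covered at 0.33.

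**What each version flags.** Write b for baseline and p for the post-baseline value.

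- As written: p < 0.47 and b ≥ 0.47.
- Male form at 0.47: p > 0.47 and b ≤ 0.47.

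| b to p | As written | Male form |
|---|---|---|
| 0.42 to 0.50 | no | yes |
| 0.46 to 0.48 | no | yes |
| 0.48 to 0.42 | yes | no |

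No pair can satisfy both versions, because one needs p below 0.47 and the other p above it.

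**Count on a grid.** Take b and p in hundredths from 0.25 to 0.60, which gives 36 × 36 = 1,296 pairs. This illustrates the logic and is not a patient distribution.

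- Rises from ≤0.47 to >0.47: 23 baselines × 13 post values = 299. The female row as written flags 0 of 299; with the male form it flags all 299.
- Rises of any size: 36 × 35 / 2 = 630. The female row as written flags 0.
- Falls from ≥0.47 to <0.47: 14 × 22 = 308. The second line as written flags all 308. Of these, 14 × 8 = 112 end below 0.33 and are flagged by the first line anyway, so the misprint adds 308 − 112 = 196.
- Comparator: the male row flags all 224 grid rises from ≤0.52 to >0.52.

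**Missing baseline (SAP 6.3), applying only the post-baseline condition.** The second line as written flags every female value below 0.47. A value of 0.40 is flagged as written and not under the male form; 0.50 is the reverse.

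**Unit pairs in the same table.** The unfasted glucose pair, 10 mmol/L and 180 mg/dL, gives a factor of 180 / 10 = 18.

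- *Fasted glucose:* 7 × 18 = 126 mg/dL, not 120; 120 / 18 = 6.67 mmol/L. A change from 100 to 122 mg/dL is flagged only by the mg/dL version, and 122 to 130 only by the mmol/L version.
- *Hypoglycaemia:* 2.7 × 18 = 48.6 mg/dL, against a stated 50. A fall from 80 to 49 mg/dL is flagged only in mg/dL.
- *Low calcium:* the high pair gives 11.6 / 2.9 = 4.0, so 2 mmol/L is 8 mg/dL and only the signs differ. A fall from 9.0 to 8.0 mg/dL is flagged only in mg/dL, and 8.0 to 7.8 only in mmol/L.
- *Hemoglobin:* the baseline condition is above 10 in g/dL but at or above 100 in g/L. A fall from 10.0 to 9.5 g/dL is flagged only in g/L.
- *Triglycerides:* the row's own factor gives 5 g/L × 1.14 = 5.70 mmol/L for 500 mg/dL, against a stated 5.64.

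**The case against.** The best case on the other side is about weight. This is one evident slip in one descriptive row. It applies alike to all three arms, and no test depends on it. High female values would not vanish, because SAP 5.8.2 also provides:

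- "Descriptive statistics of laboratory result and change from baseline by visit";
- a summary of "patients with abnormal lab value during study whose screening and baseline values are normal";
- "Listing of all laboratory parameters normal range, abnormal flag and treatment-emergent PCSV by patient and visit will be provided".

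Protocol 9.5.3.2 also flags out-of-range values in listings, and Protocol 6.2.3.5 has the investigator review every result. All of this stands and limits the reach. It does not make the PCSV count right.

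Three narrower objections also have force:

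- *Missing baseline.* Hematology is scheduled at screening and at baseline, and SAP 6.1 takes the latest valid pre-dose value, including data from rescreening. A treated patient with no baseline hematocrit should be rare.
- *The general definition.* The wording in SAP 5.8 does not by itself prove the error, since Appendix 10.3 decides what counts as a PCSV. The proof is the pattern of the table.
- *Intent.* The documents nowhere else state 0.47 as a female upper limit, so the direction is inferred. The inference is strong: a rendering fault would have to flip two different symbols in one line and leave the male line intact. A look at the approved table and the sponsor's source criteria would settle it.

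The unit pairs are a separate, smaller matter. The fasted-glucose mismatch bites only if fasting status is recorded, and the laboratory sections (Protocol 6.2.3.5, SAP 4.5.2) do not mention it. The calcium and hemoglobin differences arise only at the boundary value.

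**Conclusion.** The concern holds. As written, the female hematocrit row cannot flag any rise from at or below 0.47 to above it, and it flags falls from 0.47 or above that the 0.33 rule would not. This follows from the inequalities alone and needs no assumption about the data. That the line was meant as a high rule is an inference from the rest of the table.

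The number of patients affected cannot be given, because the documents contain no hematocrit distribution; it may be zero. The effect is confined to descriptive PCSV counts and flags. It is still worth correcting, because this cell is the operative specification for that output.

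**What to change.** Change the second female line to above 0.47 v/v with baseline at or below 0.47 v/v, the same form as the male high rule, after confirming the limit against the sponsor's source criteria.

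In the same edit:

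- State which unit system governs PCSV flagging.
- Reconcile the fasted-glucose pair to one equivalent value; the choice of value is the sponsor's.
- Align the hypoglycaemia, low-calcium, hemoglobin-baseline and triglyceride pairs.

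The cost is a few cells in one appendix table and one sentence, before programming. SAP section 1 allows revision on blinded review before the final database lock. Neither data collection nor the design changes.
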